5.4.4.2 Hepatic Function Abnormal

If laboratory testing for a subject enrolled in the study and receiving the study drug reveals an increase in serum aminotransferase (ALT, AST) $> 3 \times \text{ULN}$ or TBL $> 2 \times \text{ULN}$, at least 4 parameters (ALT, AST, ALP, and TBL) of the usual hepatic function test parameters should be retested. The retest should be performed between 48 hours and 72 hours after notification of the test results.

For additional information on monitoring and the assessment of the hepatic function test, see Appendix 4 “Liver Safety Monitoring and Assessment.”

If laboratory testing for a subject enrolled in the study receiving the study drug reveals an increase in serum aminotransferase (ALT, AST) $> 3 \times \text{ULN}$ and TBL $> 2 \times \text{ULN}$, the investigator will determine whether it is an SAE. Even if the abnormality is not considered an SAE by the investigator/sub-investigator, it will be reported to the sponsor or CRO in writing as in the case of SAEs.

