5.5.2 Definition of Serious Adverse Events (SAEs)

An adverse event is considered “serious” if, in the view of either the investigator or Sponsor, it results in any of the following outcomes:

- Results in death
- Is life threatening (an adverse event is considered “life-threatening” if, in the view of either the investigator or Sponsor, its occurrence places the subject at immediate risk of death. It does not include an adverse event that, had it occurred in a more severe form, might have caused death)
- Results in persistent or significant disability/incapacity or substantial disruption of the ability to conduct normal life functions
- Results in congenital anomaly, or birth defect
- Requires inpatient hospitalization or leads to prolongation of hospitalization (hospitalization for treatment/observation/examination caused by AE is to be considered as serious)
- Other medically important events

Medical and scientific judgment should be exercised in deciding whether expedited reporting is appropriate in other situations, such as important medical events that may not be immediately life-threatening or result in death or hospitalization but may jeopardize the subject or may require intervention to prevent one of the other outcomes listed in the definition above. These events, including those that may result in disability/incapacity, should also usually be considered serious. Examples of such events are intensive treatment in an emergency room or at home for allergic bronchospasm; blood dyscrasias or convulsions that do not result in hospitalization; or development of drug dependency or drug abuse.

In addition, all sponsor’s clinical studies have the requirement that all the medical events described in Appendix 3 “Events Always considered to be Serious” and Appendix 4 “Liver Safety Monitoring and Assessment” be reported by the investigator as SAEs even if they do not meet the aforementioned conditions.

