APPENDIX <3>: EVENTS ALWAYS CONSIDERED SERIOUS

If any of the following events occurs during the study, it should be regarded as an SAE and must be reported in accordance with Section [5.5.5](#) Reporting of Serious Adverse Events (SAEs).

- Acute hepatic failure
- Renal failure acute
- Acute respiratory failure
- Agranulocytosis
- Anaphylactic reaction, anaphylactic shock
- Malignant tumor
- Aplastic anaemia
- Endotoxic shock (confirmed or suspected)
- Confirmed or suspected transmission of infectious agents by marketed product
- Congenital anomalies
- Hepatic necrosis
- Malignant hypertension
- Pulmonary fibrosis
- Pulmonary hypertension
- Sclerosing syndromes
- Convulsion (only central neurological seizure)
- Torsades de pointes
- Toxic epidermal necrolysis
- Ventricular fibrillation

Note: Hy's Law cases should be regarded as SAE.

See Appendix 4 "Liver Safety Monitoring and Assessment."

- CONFIDENTIAL -

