APPENDIX <4>: LIVER SAFETY MONITORING AND ASSESSMENT

If laboratory testing for a subject enrolled in the study and receiving the study drug reveals an increase in serum aminotransferase (ALT, AST) $> 3 \times \text{ULN}$ or TBL $> 2 \times \text{ULN}$, the investigator/sub-investigator should repeat at least 4 parameters (ALT, AST, ALP, and TBL) of the usual hepatic function test parameters. Retesting should be performed between 48 hours and 72 hours after notification of the test results. For studies for which a central laboratory () is used, alerts will be generated by the central laboratory regarding moderate and marked liver abnormality to inform the investigator or other responsible personnel and the sponsor. Subjects should be asked if they have any symptoms suggestive of hepatobiliary dysfunction by the investigator/sub-investigator.

Definition of Hepatic Function Abnormal

Confirmed hepatic function abnormal will be characterized as moderate (hepatocellular failure type or cholestasis type) or marked (mixed type) based on the ULN as follows:

	ALT or AST		TBL
Moderate			
Hepatocellular failure type	$> 3 \times \text{ULN}$	or	$> 2 \times \text{ULN}$
or			
cholestasis type			
Marked			
Mixed type	$> 3 \times \text{ULN}$	and	$> 2 \times \text{ULN}$

In addition, the subject with any of the following should be considered to have marked (severe) hepatic function abnormal.

ALT or AST $> 8 \times \text{ULN}$

ALT or AST $> 5 \times \text{ULN}$ for more than 2 weeks

ALT or AST $> 3 \times \text{ULN}$ and INR > 1.5

ALT or AST $> 3 \times \text{ULN}$ with the appearance of fatigue, nausea, vomiting, right upper quadrant pain or tenderness, pyrexia, rash and/or eosinophilia ($> 5\%$)

If the investigator/sub-investigator determines that abnormal liver function results, other than as described above, qualify as moderate or marked abnormalities, they should conduct additional monitoring and follow-up.

Follow-up Procedures

Confirmed moderate and marked hepatic function abnormal should be thoroughly characterized by obtaining appropriate expert consultations, detailed pertinent history, physical examination and laboratory tests by the investigator/sub-investigator. The investigator should complete the liver abnormality case report form (LA-CRF) or an appropriate document. Subjects with confirmed abnormal liver function test results should be followed as described below by the investigator/sub-investigator.

- CONFIDENTIAL -

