If moderate liver abnormality is confirmed, re-testing should be performed every 2 to 3 times a week. If the abnormal test values stabilize or the patient is asymptomatic after the study drug is withdrawn, re-testing should be performed at a frequency of once a week or less.

Marked hepatic function abnormal, in the absence of another etiology, may be considered an important medical event and reported as an SAE by the investigator. The sponsor should be contacted and informed of all subjects for whom marked hepatic function abnormal possibly attributable to study drug is observed.

To further assess the findings of hepatic function abnormal, the investigator/sub-investigator is expected to:

Obtain a more detailed history of symptoms and prior or concurrent diseases. Symptoms and new onset-diseases should be recorded as “AEs” on the AE page of CRF. Illnesses and conditions such as hypotensive events, and decompensated cardiac disease that may lead to secondary liver abnormalities should be noted. Non-alcoholic steatohepatitis (NASH) is seen in obese hyperlipoproteinemic and/or diabetic patients and may be associated with fluctuating serum aminotransferase (ALT, AST) levels. The investigator/sub-investigator should ensure that the medical history form captures any illness that pre-dates study enrollment that may be relevant in assessing hepatic function.

Obtain a history of concomitant drug use (including non-prescription medication, complementary and alternative medications), alcohol intake, drug abuse, and special diets. Medications, including dose, should be entered on the concomitant medication page of CRF. Information on alcohol, other substance use, and diet should be entered into the LA-CRF or an appropriate document.

Obtain a history of exposure to environmental chemical agents.

Based on the subject’s history, other testing may be appropriate including:

- Acute viral hepatitis subtypes (A, B, C, D, E, or other infectious agents)
- Ultrasound or other imaging to assess biliary tract disease
- Other laboratory tests including INR, direct bilirubin

Consider gastroenterology or hepatology consultations

Enter the results for any additional testing and possible etiology into the LA-CRF or an appropriate document.

Study Discontinuation

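### SAE status of ALT/AST >3×ULN with bilirubin >2×ULN is required by Protocol 5.5.2 but discretionary in 5.4.4.2 and Appendix 4, so serious-TEAE counts depend on which passage a site follows

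*Protocol*

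**What the plan says.** Four places in the protocol bear on whether this laboratory pattern is an SAE.

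- **Section 5.5.2** says that all events described in Appendix 3 and Appendix 4 must "be reported by the investigator as SAEs even if they do not meet the aforementioned conditions".
- **Appendix 3** ends its list of always-serious events with "Note: Hy's Law cases should be regarded as SAE" and refers the reader to Appendix 4.
- **Section 5.4.4.2** names ALT/AST >3×ULN and TBL >2×ULN and says "the investigator will determine whether it is an SAE". For a case not judged to be an SAE, it adds that "it will be reported to the sponsor or CRO in writing as in the case of SAEs".
- **Appendix 4** says a marked abnormality with no other cause "may be considered an important medical event and reported as an SAE by the investigator".

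Appendix 4 also supplies the grading. Confirmed abnormalities are "characterized as moderate (hepatocellular failure type or cholestasis type) or marked (mixed type) based on the ULN as follows". Either elevation alone is moderate and both together are marked. Four further criteria also count as marked.

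On the analysis side, SAP 7.5.1.1 and SAP Appendix 3 tabulate serious TEAEs, drug-related serious TEAEs, and the subsets of each that lead to permanent discontinuation. SAP 7.5.2.1 separately tabulates the combined ALT/AST and bilirubin elevation, and the moderate and marked categories, from laboratory values.

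**The concern.** Seriousness is a recorded attribute of an adverse event, and the SAP's serious-TEAE tables depend on it. If one passage requires the attribute and another leaves it to judgement, two of the roughly 150 centres can record the same liver case differently and both be following the protocol. The recorded difference would then reflect which page the site consulted and not a difference between patients. Combined transaminase and bilirubin elevation is the pattern that Appendix 4 grades as marked, and the drug is given on top of methotrexate. A reader of the report will therefore look at the serious hepatic count. The expected number is presumably small, so one or two classification choices could decide whether that count is zero.

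**Working it through.** No figure in the plan needs reproducing. The check compares the passages and traces one case into the tables.

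**Step 1: do the passages concern the same pattern?** Section 5.4.4.2 states the thresholds directly. Appendix 4 uses the same thresholds for its marked, mixed-type category. Section 5.5.2 states no thresholds but names Appendix 4 as a whole, so it covers the pattern by cross-reference. Appendix 3 gives no thresholds; it uses the term Hy's Law, which Appendix 4 never uses. The tally is therefore one section that requires SAE reporting, one note that requires it for an undefined category, and two passages that leave it open.

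**Step 2: follow one case with ALT >3×ULN and TBL >2×ULN.**

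| Passage the site follows | Recorded as SAE? | In the serious-TEAE tables? | In the SAP 7.5.2.1 laboratory tables? |
|---|---|---|---|
| 5.5.2 | Yes | Yes | Yes |
| Appendix 3 | Yes, if the site regards it as a Hy's Law case | Depends on that reading | Yes |
| 5.4.4.2 | Investigator's choice | Either | Yes |
| Appendix 4 | Optional | Either | Yes |

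The last column assumes both elevations come from the same sample, as SAP 7.5.2.1 requires for its combinations.

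**Step 3: does anything in the SAP restore the case to the serious tables?** SAP 7.5.1 gives no rule that turns the laboratory pattern into a serious event. The events of special interest in SAP Appendix 8 have no hepatic category. Protocol 5.5.1 treats a laboratory abnormality as an AE only if a listed criterion is met, one of which is the investigator's opinion that it is clinically significant. A case could therefore lack an AE record altogether.

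**Step 4: how far does 5.5.2 reach?** Its reference to Appendix 4 is unrestricted, and that appendix also describes moderate abnormalities. The only sentence in Appendix 4 about SAE reporting concerns marked ones. Section 5.5.2 does not say which set it means.

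**Step 5: size.** The planned arm is 170 patients, and 1/170 = 0.0059, or about 0.6%. This shows what one reclassified case would do. It is not a forecast, because neither document gives an expected rate for the pattern.

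**The case against.** The best defence is that the passages agree on what matters operationally. Section 5.5.2 has the case reported as an SAE, and 5.4.4.2 has even a case judged not serious sent in writing in the same way. Protocol 5.4 requires contact within 24 hours for a marked abnormality, and Appendix 4 has the central laboratory alert the sponsor. Section 5.5.2 also makes an event serious "if, in the view of either the investigator or Sponsor, it results in any of the following outcomes", so the site does not decide alone. SAP 7.5.2.1 counts the pattern by treatment group whatever the seriousness field says. All of this stands, and it limits the point to classification. It does not remove it. The laboratory tables carry neither seriousness nor causality, and the SAP's AE sections do not say whose view is tabulated when investigator and sponsor differ. Appendix 4 makes even the SAE report optional, and does so for cases with no other explanation.

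Four stronger readings are tempting but not supported:

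- **That two places expressly make this pattern an SAE.** Only 5.5.2 does, by cross-reference. Equating Hy's Law with these thresholds needs a definition that the documents do not give.
- **That such cases vanish from the safety report.** They do not, because of the laboratory tables and the written report.
- **That 5.5.2 was meant to make moderate abnormalities SAEs.** The literal wording allows this, but Appendix 4 speaks of SAE reporting only for marked ones. What is established is an unstated scope.
- **That the Phase IIb study shows how many to expect.** Its SAE counts (1+1+2+3+0 = 7 subjects of 281) are for all causes, from 12 weeks of single-agent treatment. They give no hepatic rate.

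**Conclusion.** The conflict is real. Section 5.5.2 cannot be followed together with the discretion in 5.4.4.2 and Appendix 4, and the undefined term in Appendix 3 does not settle it. The same case can be counted or omitted in the serious, drug-related serious and serious-leading-to-discontinuation tables.

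The consequence is limited. It affects no efficacy endpoint, hypothesis test or analysis set, and the sponsor should learn of every such case. A report could nevertheless show a marked case in the laboratory table and no serious hepatic event in the AE table, with nothing to explain the difference. One case in 170 (0.6%) would be enough. The conclusion assumes that the serious-TEAE tables use seriousness as recorded, since the SAP states no other rule, and that at least one such case occurs, which the documents give no basis to predict. It deserves correction because it can change a reported safety count at little cost.

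**What to change.** 1. Reconcile Protocol 5.4.4.2, 5.5.2, Appendix 3 and Appendix 4 so that ALT/AST >3×ULN with TBL >2×ULN has one seriousness rule. The choice of rule belongs to the sponsor; the requirement is that all four passages state the same one.
2. Define Hy's Law case by reference to the laboratory criteria in Appendix 4.
3. State in 5.5.2 which Appendix 4 abnormalities it covers: moderate, marked mixed type, or the wider marked list. SAP 7.5.2.1 uses only the mixed-type definition of marked.
4. Before unblinding, list every laboratory-defined marked case under SAP 7.5.2.1. Query each one whose AE record is absent or whose seriousness differs from the reconciled rule.

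The cost is protocol wording, a memo to sites and one data query built on a category the SAP already defines. The SAP is dated 18 January 2018 and the planned study period ends that month, so revised wording may come too late to guide sites. The query would still work if it is done before the code is broken.

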5.4.5 Physical Examination

A physical examination will be performed at scheduled visits and early termination to confirm physical findings.

Physical findings and RA symptoms will be confirmed at unscheduled visits whenever possible.

5.4.6 12-lead Electrocardiogram (ECG)

A 12-lead ECG will be obtained at screening and on the assessment dates specified in the Schedule of Assessments. The investigator/sub-investigator will confirm the ECG chart, assess the results as “normal,” “abnormal but not to a clinically important degree,” or “clinically important abnormality,” and record the results of the assessment in the CRF. If the finding is “abnormal but not to a clinically important degree” or “clinically important abnormality,” the finding will be recorded in the CRF.

The screening 12-lead ECG must be performed within 4 weeks prior to the first dose of study drug. In addition, the clinical interpretation of the results of this examination must be completed prior to the first dose of study drug.

5.4.7 Radiography

Chest radiography will be performed at screening and on the assessment dates specified in the Schedule of Assessments. Chest radiography examination will be performed at early termination if it is determined necessary by the investigator/sub-investigator. However, chest radiography at screening is not required provided that there is documentation of a normal chest radiograph within 90 days of baseline. The investigator/sub-investigator will confirm the chest radiographic images, assess the results as “normal,” “abnormal but not to a clinically important degree,” or “clinically important abnormality,” and the investigator/sub-investigator record the results of the assessment in the eCRF.

- CONFIDENTIAL -

If the results of chest radiography at screening reveal findings of tuberculosis, the subject's eligibility will be decided in accordance with Exclusion Criterion 13.

5.4.8 Central ECG

Central ECG is conducted as sub-study at the sites which approved blood sampling for post-dose drug concentration. Subjects in the reference group will be excluded from Central ECG. Central ECG is performed at baseline before study drug administration, as well as before study drug administration and 2 hours after study drug administration at Week 4 or Week 8 on the same day as blood sampling for post-dose drug concentration at Week 4 or Week 8. 12-lead ECG is performed as Central ECG. The measurement date and time of central ECG is recorded in the eCRF.

The measuring and transmittal method of Central ECG in the handling manual provided by sponsor is followed. The QT interval, QTcF, and QTcB will be calculated by the third party using the Central ECG data transmitted and the method of ECG analysis is described in the handling manual prepared by the third party.

5.5 Adverse Events and Other Safety Aspects

5.5.1 Definition of Adverse Events (AEs)

An AE is defined as any untoward medical occurrence in a subject administered a study drug or has undergone study procedures and which does not necessarily have a causal relationship with this treatment. An AE can therefore be any unintended sign (including an abnormal laboratory finding), symptom, or disease temporally associated with the use of a medicinal (investigational) product, whether or not related to the medicinal (investigational) product.

An abnormality identified during a medical test (e.g., laboratory parameter, vital sign, ECG data, physical examination) should be defined as an AE only if the abnormality meets one of the following criteria:

- Induces clinical signs or symptoms
- Requires active intervention
- Requires suspension, interruption, or discontinuation of the study drug
- The abnormality or laboratory test value is clinically significant based on the opinion of the investigator or other responsible personnel

The particulars to be noted with respect to the AE are the name of the event, date of onset, date of disappearance, severity (at peak time), seriousness, treatment of the study drug, other treatment, outcome, causal relationship to the study drug, and rationale for the assessment of causal relationship. The rationale for the assessment of the causal relationship does not need to be recorded for all AEs but only at the request of the sponsor. The severity of each event should be recorded on a scale of Grade 1 to Grade 5 in the eCRF, and the causal relationship to the study drug should be recorded as "Probable," "Possible," or "Not related" (see Section

- CONFIDENTIAL -

5.5.3 Criteria for Causal Relationship to the Study Drug and Section 5.5.4 Criteria for Defining the Severity of an Adverse Event). The treatment of the AE (whether it was treated with pharmacotherapy or by other means) and the treatment of the study drug should be recorded in the medical record or other source documents and in the eCRF. The outcome should be recorded in the medical record or other source documents and in the eCRF as “resolved,” “alleviated,” “unresolved,” “resolved but with late effects,” “death,” or “unknown.”

5.5.2 Definition of Serious Adverse Events (SAEs)

An adverse event is considered “serious” if, in the view of either the investigator or Sponsor, it results in any of the following outcomes:

- Results in death
- Is life threatening (an adverse event is considered “life-threatening” if, in the view of either the investigator or Sponsor, its occurrence places the subject at immediate risk of death. It does not include an adverse event that, had it occurred in a more severe form, might have caused death)
- Results in persistent or significant disability/incapacity or substantial disruption of the ability to conduct normal life functions
- Results in congenital anomaly, or birth defect
- Requires inpatient hospitalization or leads to prolongation of hospitalization (hospitalization for treatment/observation/examination caused by AE is to be considered as serious)
- Other medically important events

Medical and scientific judgment should be exercised in deciding whether expedited reporting is appropriate in other situations, such as important medical events that may not be immediately life-threatening or result in death or hospitalization but may jeopardize the subject or may require intervention to prevent one of the other outcomes listed in the definition above. These events, including those that may result in disability/incapacity, should also usually be considered serious. Examples of such events are intensive treatment in an emergency room or at home for allergic bronchospasm; blood dyscrasias or convulsions that do not result in hospitalization; or development of drug dependency or drug abuse.

In addition, all sponsor’s clinical studies have the requirement that all the medical events described in Appendix 3 “Events Always considered to be Serious” and Appendix 4 “Liver Safety Monitoring and Assessment” be reported by the investigator as SAEs even if they do not meet the aforementioned conditions.

